### 14.2.1.2 Figure of Normalization Proportion on COVID-19-Related Clinical Signs (Best Case Scenario)

### 14.2.1.3 Figure of Normalization Proportion on COVID-19-Related Clinical Signs (Worst Case Scenario)

*Use TTR Figure Layout*

### 14.2.1.4 Time to Oxygen Saturation Level Normalization

*Use TTR Layout*

### 14.2.1.5 Figure of Normalization Proportion on Oxygen Saturation Level (Best Case Scenario)

### 14.2.1.6 Figure of Normalization Proportion on Oxygen Saturation Level (Worst Case Scenario)

*Use TTR Figure Layout*

## 14.2.2 Covid-19-Related Symptoms

### 14.2.2.1 Time to COVID-19-Related Symptoms Resolution

*Use TTR Layout*

### 14.2.2.2 Figure of Recovery Proportion on COVID-19-Related Symptoms (Best Case Scenario)

### 14.2.2.3 Figure of Recovery Proportion on COVID-19-Related Symptoms (Worst Case Scenario)

*Use TTR Figure Layout*

## 14.2.3 Nasopharyngeal Swab RT-PCR Result and SARS-CoV-2 Viral Load

### 14.2.3.1 SARS-CoV-2 Viral Clearance and Viral Load [copies/µL]

Population: Intent-to-Treat Population / Per-Protocol Population

Characteristics	Treatment Group	Difference	P-value
--Repeat Population: <See populations above>			
. Repeat Visit:			
Visit 1 (Screening), Baseline, Visit 4 (Day 8), Visit 6 (Day 14, EOT), Visit 7 (Day 28, F1), LOCF			
N (Missing)	XXX (XXX)		
Negative	XXX (XXX.X%)		
Positive	XXX (XXX.X%)		
N (Missing)	XXX (XXX)		0.XXXX
Mean (SD)	XXX (XXX)		
Median (IQR)	XXX (XXX)		
Q1~Q3	XXX~XXX		
Min~Max	XXX~XXX		
Repeat [Baseline to Visit] except Visit 1 (Screening) and Baseline			C/F
N (Missing)	XXX (XXX)	0.XXXX	
Positive to Negative#	XXX (XX.X%)		
Positive to Positive	XXX (XX.X%)		
Diff. between groups	§C - §S		
Difference (#)	XXX%		
95% CI (#)	XXX% ~XXX%a		
Repeat [Visit - Baseline] except Visit 1 (Screening) and Baseline			TW
N (Missing)	XXX (XXX)	0.XXXX	
Mean (SD)	XXX (XXX)		
Median (IQR)	XXX (XXX)		
Q1~Q3	XXX~XXX		
Min~Max	XXX~XXX		
For W, normality is not applied			
Groups Diff	§C - §S		
Median (Asymptotic SE)	XXX		
95% CI (HL)	XXX~XXX		
For T, normality is applied			
Groups Diff	§C - §S		
Mean (SD)	XXX (XXX)		
95% CI	XXX~XXX		

a denotes CI using normal approximation for binomial proportion of #  
 Viral Load > 25,000.00 copies/µL is estimated as 25,000.00 copies/µL.  
 Baseline is Visit 2 (Day 1) data, or is Visit 1 if Visit 2 (Day 1) is null

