### 1.4.3 Method for Continuous Data

Demographics, baseline characteristics and continuous efficacy data will be analyzed by using two sample t test or Wilcoxon rank-sum test as appropriate. Net changes from pre-treatment laboratory test results and vital signs will be analyzed by using ANCOVA model with baseline value as covariate or Wilcoxon rank-sum test as appropriate.

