#### 3.1 Analysis of Continuous Data

For ANOVA / ANCOVA / T test (two sample t test) noted in the mock-up table, Wilcox\_t (Wilcoxon rank-sum test in t approximation) will be applied if normality assumption is not valid (p-value of Shapiro-Wilk normality test  $\leq 0.05$ ).

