#### 3.2 Analysis of Categorical Data

C/F noted in the mock-up table, Chi-Square test is applied when no cell have expected count  $< 1$  and  $<= 20\%$  of the cells are with expected count  $< 5$ , otherwise Fisher's exact test will be applied.

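### Viral-load change is tested in raw copies/µL with no baseline adjustment, so after falls of about 2 log10 or more that row largely compares baseline loads

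*SAP*

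**What the plan says.** The table headed "SARS-CoV-2 Viral Clearance and Viral Load [copies"/µL] in SAP 14.2.3.1 has a row "Repeat [Visit - Baseline] except Visit 1 (Screening) and Baseline", marked for t test or Wilcoxon. It is summarised by a mean difference or a Hodges-Lehmann interval, at Day 8, Day 14, Day 28 and LOCF. A footnote sets results of "Viral Load > 25,000.00 copies"/µL to 25,000.

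SAP 1.4.3 matches the table: "continuous efficacy data will be analyzed by using two sample t test or Wilcoxon rank-sum test as appropriate". The same section treats other data differently: "Net changes from pre-treatment laboratory test results and vital signs will be analyzed by using ANCOVA model with baseline value as covariate", or Wilcoxon. Under SAP 3.1 the Wilcoxon test "will be applied if normality assumption is not valid", judged by Shapiro-Wilk p ≤ 0.05.

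Neither document mentions a log scale, a ratio to baseline, or a numeric value for a negative result. Quantitative change in viral load is one of three virologic measures under the antiviral objective (Protocol 1.1 and Section 3), and its scale is not specified.

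In the same table, the interval for the difference in conversion carries the note "a denotes CI using normal approximation for binomial proportion of" the marked category.

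**The concern.** Viral load can span orders of magnitude, and an antiviral effect acts roughly as a multiplier. On the raw scale a patient who starts high dominates the difference, and how far the load then falls hardly registers. If that happens at Day 8, 14 or 28, the only change-from-baseline test of quantitative viral load mostly reports which arm started higher. With about 10 patients per arm (Protocol 9.3), chance imbalance in starting load is plausible. A real antiviral difference could then be reported as no difference on this row.

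**Working it through.** The documents give no power, mean, SD, expected fall or detection limit for viral load, so there is no stated figure to reproduce.

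**Arithmetic, with no assumptions.** If load falls by k log10, visit load = baseline × 10^−k, so raw change = −(1 − 10^−k) × baseline.

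- k = 0.5: 1 − 0.316 = 68% of minus baseline
- k = 1: 90%
- k = 2: 99%
- k = 3: 99.9%
- load set to zero: 100%

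Example: 20,000 to 200 (2 log10) is −19,800 and 20,000 to 20 (3 log10) is −19,980. These are almost the same, although residual virus differs tenfold. But 200 to 2, also 2 log10, is −198.

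**How closely raw change follows baseline.** Assumed: baseline mean 3 log10, SD 1.0 to 1.5, SD of fall 0.5 to 1.0, cap 25,000. The correlation of raw change with minus baseline is:

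- 0.96 to 0.999 at a mean fall of 3 log10
- 0.86 to 0.99 at 2 log10
- 0.62 to 0.85 at 1 log10
- 0.45 to 0.60 at 0.5 log10

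The rank correlation at 2 log10 is 0.83 to 0.99, so switching to Wilcoxon ranks nearly the same quantity.

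**Effect of an imbalance.** Assumed: 10 per arm, baseline SD 1.0, SD of fall 0.5, equal 2 log10 falls, baselines 1 log10 apart. The raw-change test rejects in 45% of replicates and a direct test of baseline in 51%. Log10 ANCOVA rejects in 4%.

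**Power for an extra fall of 1.5 log10.** Assumed: 10 per arm, baseline SD 1.2, SD of fall 1.0, cap 25,000. The SAP rule is applied with undetected results set to 0. The log10 rule is ANCOVA on log10 change, with an unadjusted Wilcoxon on log10 change if residual normality fails and undetected results set to half the limit. Entries are % at baseline means 2.5/3.5/4.5 log10 and carry simulation error of a few points.

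| Control fall (log10) | Detection limit (copies/µL) | SAP rule | Log10 rule |
|---|---|---|---|
| 2.0 | 0.1 | 3/7/17 | 74/82/74 |
| 2.0 | 1 | within 3 to 19 | 58/70/71 |
| 2.0 | 10 | within 3 to 19 | 27/52/64 |
| 3.0 | 0.1 | 3/5/10 | 54/70/69 |
| 3.0 | 10 | 4 to 10 | 11/26/48 |
| 1.0 | 0.1 | 8/14/33 | 83/83/74 |
| 0.5 | 0.1 | 20/27/45 | 86/83/73 |

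For an extra 1.0 log10 (control fall 2.0, limit 0.1) the figures are 2/6/10 against 44/47/42. With no true effect (limit 0.1), the SAP rule rejects in 3 to 6% and the log10 rule in 4 to 6%.

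**Why the fallback must be adjusted.** If every patient is undetected, log10 change is a constant minus log10 baseline, so an unadjusted rank test again compares baselines. Flooring also makes residuals non-normal: the fallback was triggered in up to 84% of replicates when many results were undetected. At limit 10 and control fall 2.0, rank ANCOVA gave 38% against 27% (baseline mean 2.5) and 62% against 52% (mean 3.5).

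**Separate minor check, conversion interval.** SAP 3.2 says "Chi-Square test is applied when no cell have expected count" below 1 and at most 20% of cells are below 5. In a 2×2 table at 10 v 10, all four expected counts must then be at least 5, which needs exactly 10 conversions in total; otherwise Fisher applies. For 10/10 v 7/10 the Wald interval is 30% ± 1.96 × √(0.7 × 0.3/10) = 30% ± 28.4%, or 1.6% to 58.4%. It excludes zero beside a Fisher p of 0.21. Newcombe gives −3.8% to 60.3%. Over true rates of 5 to 95% per arm, mean coverage is 90.4% for Wald, 95.2% for Newcombe and 95.8% for Miettinen-Nurminen.

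**The case against.** The harm depends on a fall that the documents do not state. At 1 log10 or less the row still carries follow-up information. Even at a control fall of 2 log10, the median rank correlation with minus baseline was only 0.72 when baselines averaged 4.5 log10, close to the cap. That stands, and the point is worded accordingly.

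The row also carries little weight. The study is an unpowered proof of concept (Protocol 9.3), and the protocol planned no inference (9.8.4) until SAP 1.4.1 added it. Conversion and time to clearance do not depend on the scale. SAP 14.2.3.1 also has an unlabelled p-value slot beside the by-visit loads. If used after baseline it would recover part of the power, roughly 40 to 48% for 1.5 log10 at a control fall of 2.0 and limit 0.1. But no test is named there, and the matching slots for EQ-5D-5L (14.2.5.1) and laboratory tests (14.3.6) are for baseline only. This limits the harm without repairing the change row.

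It might be said that viral load is a laboratory result and so already gets ANCOVA. The table marks this row for t test or Wilcoxon, so that reading does not hold.

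The strongest objection concerns the remedy. A reader might infer that a log10 analysis would usually detect a 1.5 log10 effect. The documents give no detection limit, and at 10 copies/µL several settings fall to about half or well below. What stands is that log10 was never worse for a true effect in the settings tried.

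On the minor point, the conversion row covers baseline-positive patients with a result at that visit, so 10 v 10 is about the most it can hold.

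**Conclusion.** The point holds as a loss of sensitivity on one exploratory secondary row. The dependence on baseline is arithmetic and certain. Its practical size depends on falls of about 2 log10 or more, or on loads set to zero. The power figures rest wholly on assumed means, SDs, falls and detection limits.

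Two stronger readings are not supported. A reader might infer that the row produces false antiviral claims. It does not: over randomisations the null rejection rate is 3 to 6%, and the 45% figure describes what happens given a large imbalance. A reader might also infer that the antiviral objective as a whole is compromised; its other two measures are untouched. The row should be corrected because doing so is cheap and the SAP already adjusts comparable data for baseline.

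**What to change.** In SAP 14.2.3.1, replace the test on the change row with: change from baseline in log10 viral load by ANCOVA with treatment and baseline log10 viral load; if Shapiro-Wilk p ≤ 0.05 on the model residuals, rank ANCOVA (rank of visit viral load on treatment and rank of baseline viral load).

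State the value used for undetected results, for example half the assay's detection limit, and that results above 25,000 are set to 25,000 before the log. Keep raw copies/µL as description with no p-value. Name the test for the by-visit p-value slot, or mark it baseline only.

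Separately, and minor: replace the normal-approximation interval for conversion with Newcombe or Miettinen-Nurminen. Of 55 one-direction tables at 10 v 10, Wald disagrees with the SAP p-value in 12 and each alternative in 6, so conflict is reduced but not removed. The new interval is usually somewhat wider.

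Cost: SAP wording and a few lines of code, with no new data. Results are then read as log10 differences, and a 1.0 log10 effect would still often be missed. When most patients are undetected no change analysis is informative, and conversion should carry the interpretation.

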	
evaluated daily from randomization (Day 1) through Day 14 and at Day 28 and Day 45.
 
Note: Each symptom is scored individually using the following response options and scoring values:
 
○ Items 1–18: None = 0; Mild = 1; Moderate = 2; and Severe = 3○ Items 19 and 20: Not at all = 0; 1–2 times = 1; 3–4 times = 2; 5 or more times = 3○ Items 21–22: The same as usual = 0, Less than usual = 1, NO sense of smell/taste = 2. 
Note: If some symptoms were caused by other conditions documented in the medical history and started before COVID-19 (e.g., insomnia), the patient can be considered as recovered, when these symptoms return to the previous (pre-COVID-19) value.

To evaluate preliminary evidence of anti-viral activity of CX-4945 as compared to the control arm.	
Change in virologic measure:
 
● Proportion of patients with conversion of positive RT-PCR to negative RT-PCR from Randomization (Day 1) through Day 28.● Time to SARS-CoV-2 viral clearance measured as number of days from positive RT-PCR collected at randomization (Day 1) to negative RT-PCR.● Quantitative changes in viral load from Randomization (Day 1) to Day 28. 
Note: RT-PCR/viral load tests will be performed at Randomization (Day 1) and then on Day 8, Day 14 and Day 28.

To evaluate the PK of CX-4945 when given at 1000 mg BID PO (Treatment Arm A only)	
● Plasma sample of CX-4945 are collected at the following timepoints from the first four patients randomized to treatment arm A:
○ Day 1: pre-dose, 1, 2, 3, 6 and 24 hours post Day 1 morning dose.

	
○ Day 14: pre-dose, 1, 2, 3, 6, 24, 48 and 72 hours post Day 14 morning dose. 
Note: The following PK parameters will be calculated: Cmax, Tmax, AUC_{0-t}, AUC₀₋₆, and T_{1/2}.

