9.3. SAMPLE SIZE DETERMINATION AND RATIONALE

A total of approximately 20 subjects will be randomized 1:1 in this study. The sample size is based on clinical judgment. No statistical power calculation is used to establish the sample size for this proof-of-concept study.

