**For CI and p-value (between groups):**

Wilcox\_t denotes Wilcoxon rank-sum test (Mann-Whitney U Test) in t approximation

Wilcox\_z denotes Wilcoxon rank-sum test (Mann-Whitney U Test) in z approximation

ANOVA denotes Treatment effect in ANOVA model

ANCOVA denotes Treatment effect in ANCOVA model

For 95% CI (HL), HL denotes CI using Hodges-Lehman for median

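### The 95% CI for the between-arm difference in RT-PCR conversion uses a normal approximation with about 10 patients per arm and no small-sample alternative

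*SAP*

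**What the plan says.** Protocol section 3 lists as a secondary antiviral endpoint "Proportion of patients with conversion of positive RT-PCR to negative RT-PCR from Randomization (Day 1) through Day 28". Protocol 9.3 sets the size: "A total of approximately 20 subjects will be randomized 1:1 in this study", and adds that "No statistical power calculation is used to establish the sample size for this proof-of-concept study".

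SAP table 14.2.3.1 analyses this endpoint at Days 8, 14 and 28 and at LOCF, in the ITT and PP populations. Under "Diff. between groups" it prints the CX-4945 minus SOC difference in the proportion going from positive to negative, with a 95% CI. The CI carries marker a, and the footnote says "a denotes CI using normal approximation for binomial proportion of" the flagged row.

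The p-value for the same rows follows the chi-square/Fisher rule of SAP 3.2: "Chi-Square test is applied when no cell have expected count" below 1 and no more than 20% of cells fall below 5; "otherwise Fisher's exact test will be applied".

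For the viral-load change in the same table, the interval follows the test that is chosen. When the Wilcoxon test is used, the Instructions and Abbreviations say "For 95% CI (HL), HL denotes CI using Hodges-Lehman for median". No counterpart is given for a difference in proportions.

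**The concern.** The SAP accepts that large-sample methods may fail here: it has a sparse-table rule for the p-value and a nonparametric interval for the continuous outcome. The conversion difference is the one quantity in this table whose interval stays on the large-sample formula whatever the counts.

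A Wald interval takes its standard error from the observed proportions. When those are 0% or 100% the standard error contribution vanishes, so the interval is shortest where 10 patients say least about the true rate. By Day 28 high conversion in both arms is a realistic possibility.

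The interval appears eight times in the report (three visits plus LOCF, two populations). One that excludes zero could be quoted as a sign of antiviral activity although the p-value beside it gives no support.

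**Working it through.** **Inputs.** About 20 patients randomized 1:1 (Protocol 9.3), so n = 10 per arm. Two-sided 95% level and CX-4945 minus SOC contrast (SAP 14.2.3.1). Test rule from SAP 3.2. The documents state no conversion rates and no power calculation, so there is no figure of the plan's own to reproduce; every true rate below is an assumption. Footnote a is read as an unpooled Wald interval without continuity correction, because the SAP mentions none.

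**Step 1: how often the SAP's rule rejects the large-sample test.** In a 2x2 table one cell is already 25% of cells, so chi-square needs all four expected counts to be at least 5. With t conversions among 20 patients the expected counts are t/2 and (20 - t)/2. Both reach 5 only at t = 10. That is 11 tables (0+10, 1+9, ..., 10+0) out of 11 x 11 = 121, so 121 - 11 = 110 go to Fisher.

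If either arm has 9 or fewer evaluable patients, its two expected counts sum to less than 10, so one is below 5 and Fisher always applies. This can easily happen, because the conversion rows count only patients positive at baseline with a result at the visit.

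**Step 2: two example tables.** The Wald interval is p1 - p2 ± 1.96 × sqrt[p1(1 - p1)/n + p2(1 - p2)/n].

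- 10/10 versus 7/10: difference 0.30; SE = sqrt(0 + 0.7 × 0.3/10) = 0.145; 0.30 ± 1.96 × 0.145 gives 1.6% to 58.4%.
- 10/10 versus 10/10: SE = 0, so the interval is 0% to 0%.

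Newcombe combines the Wilson limits of each arm, here 0.722 to 1.000 for 10/10 and 0.397 to 0.892 for 7/10. The lower limit for 10/10 versus 7/10 is 0.30 - sqrt[(1 - 0.722)² + (0.892 - 0.7)²] = -3.8%. The upper limit is 0.30 + sqrt[0 + (0.7 - 0.397)²] = 60.3%.

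| Table | Fisher p | Wald | Newcombe | Miettinen-Nurminen |
|---|---|---|---|---|
| 10/10 vs 10/10 | 1.00 | 0% to 0% | -27.8% to 27.8% | -28.8% to 28.8% |
| 10/10 vs 7/10 | 0.21 | 1.6% to 58.4% | -3.8% to 60.3% | -3.2% to 61.0% |
| 10/10 vs 6/10 | 0.087 | 9.6% to 70.4% | 3.8% to 68.7% | 5.6% to 69.3% |

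**Step 3: all 121 tables at 10 per arm.**

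- Wald has zero width in 4 tables (each arm at 0/10 or 10/10) and a limit beyond ±100% in 14.
- The interval excludes zero while the p-value chosen by SAP 3.2 exceeds 0.05 in 24 tables for Wald, 12 for Newcombe and 12 for Miettinen-Nurminen. Of Wald's 24, 12 have p from 0.14 to 0.21 and 12 have p from 0.057 to 0.087. The score intervals remove the first group and keep the second.
- At assumed rates of 90% versus 70% such a conflict has probability 22.8% with Wald and 8.6% with Newcombe. At 80% versus 60% the figures are 18.7% and 7.3%.

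**Step 4: exact coverage**, summing binomial probabilities over all tables, for true rates of 10% to 90% in steps of 10 in each arm (81 pairs).

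| Interval | Median | Minimum | Pairs below 93% |
|---|---|---|---|
| Wald | 91.5% | 81.4% | 65 |
| Newcombe | 95.4% | 92.8% | 4 |
| Miettinen-Nurminen | 95.6% | 93.7% | 0 |

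Single Wald values: 91.2% at 50/50, 90.5% at 70/70, 92.8% at 80/60. Nearer the boundary, partly outside the grid: 87.0% at 95/80, 75.3% at 95/90, 64.0% at 99/90. Wald does not under-cover everywhere: it reaches 95.0% at 90/90 and 98.6% at 95/95. There, however, zero-width intervals occur in 12% and 36% of trials (0.9^20 = 0.12; 0.95^20 = 0.36), and they count as covering only because the true difference is exactly zero.

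**The case against.** The footnote says only that a normal approximation is used, so the size of the harm depends on the uncorrected reading. With a continuity correction of 1/n = 0.10, median coverage on the same grid is 96.9%, 4 of 81 pairs fall below 93%, and only 8 of 121 tables conflict with the p-value, fewer than for the score intervals. This stands as a limit on the coverage and conflict figures. It does not rescue the plan: the SAP states no correction, minimum coverage is still 87.7%, and the interval at 10/10 versus 10/10 is only -10% to 10%, about a third of the Newcombe width.

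Part of the disagreement with the p-value comes from Fisher's conservatism, and half of the 24 conflicts remain under either score interval. That is correct. The count of 110 of 121 weights all tables equally; it is not a probability and does not itself measure error in the interval. It shows only that the SAP's own criterion finds large-sample methods unsuitable at this size.

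The consequence is modest. The study is an unpowered proof of concept, the protocol planned no inferential statistics, no decision rule was found that uses this interval, counts and p-values stand beside it, and viral clearance is also analysed by Kaplan-Meier and log-rank methods. All of this bears on priority. None of it makes the interval right.

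**Conclusion.** The concern holds. The SAP fixes a large-sample interval for the conversion difference at about 10 patients per arm, and nothing elsewhere in the SAP or protocol repairs it. Under the uncorrected reading, nominal 95% coverage is typically about 91 to 92% and as low as 81.4% on the assumed grid. The interval can also collapse to zero width, or exclude zero beside p = 0.21.

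That the small-sample method is missing rests on the documents alone. The size of the effect rests on three assumptions: 10 evaluable patients per arm, no continuity correction, and the chosen true rates. This should be corrected before the results are reported, but it does not threaten the trial: it affects the reading of one secondary, exploratory endpoint and leaves the primary safety analysis untouched.

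**What to change.** In SAP 14.2.3.1, replace footnote a with one named small-sample interval for the CX-4945 minus SOC difference. Miettinen-Nurminen is the natural choice on the figures above, since it never falls below 93% on the grid. Newcombe is close behind. An exact unconditional interval would also answer the concern but was not evaluated here. Add a sentence saying that this interval and the Fisher p-value come from different methods and can disagree.

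The cost is one option in the SAS call and one footnote, with no change to data, endpoint or sample size. The change does not end all conflict: 12 of 121 tables, such as 10/10 versus 6/10, would still show an interval above or below zero beside p > 0.05. Nor are the new intervals uniformly wider: Newcombe is wider than Wald in 48 of the 121 tables and narrower in 73.

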### 14.2.3.2 Time to SARS-CoV-2 Viral Clearance

Use TTR Layout

### 14.2.3.3 Figure of SARS-CoV-2 Viral Clearance Proportion (Best Case Scenario)

### 14.2.3.4 Figure of SARS-CoV-2 Viral Clearance Proportion (Worst Case Scenario)

Use TTR Figure Layout

## 14.2.4 Clinical Status - NIAID 8-Point Clinical Progression Outcomes Scale

### 14.2.4.1 Clinical Status - NIAID 8-Point Clinical Progression Outcomes Scale

Population: Intent-to-Treat Population / Per-Protocol Population

Characteristics	Treatment Group	P-value
--Repeat Population: <See populations above>		
N	XXX	
Subjects with any below [Event#:Subj#]	XXX : XXX (XXX.X%)	
~ Death (NIAID item 1)	XXX : XXX (XXX.X%)	
~ Respiratory Failure (NIAID item 2~3 or from AE)	XXX : XXX (XXX.X%)	
~ Hospitalized (NIAID item 2~6)	XXX : XXX (XXX.X%)	
. Repeat Visit: No 'Visit 1 (Screening)' for IL-6: Visit 1 (Screening), Baseline, Adjusted Visit 3 (Day 4), Adjusted Visit 4 (Day 8), Adjusted Visit 5 (Day 11), Adjusted Visit 6 (Day 14, EOT), Visit 7 (Day 28, F1), Visit 8 (Day 45, F2), LOCF		
N (Missing)	XXX (XXX)	0.XXXX
Item 1	XXX (XXX.X%)	
Item 2	XXX (XXX.X%)	
...	...	
Item 8	XXX (XXX.X%)	
Repeat [Baseline to Visit] except Visit 1 (Screening), Baseline		
N (Missing)	XXX (XXX)	C/F
Improvement (Item 7 to Item 8)	XXX (XX.X%)	0.X
Progression (Item 7 to Item 1~6)	XXX (XX.X%)	XX
		X

Respiratory failure required mechanical ventilation, oxygen delivered by high-flow nasal cannula, ESMO; shock or multi-organ dysfunction/failure

For NIAID 8-Point Clinical Progression Outcomes Scale:

Item 1 - Death

Item 2~3 - Hospitalized, respiratory failure

Item 4~6 - Hospitalized, non-respiratory failure

Item 7 - Not hospitalized, limitation on activities and/or requiring home oxygen

Item 8 - Not hospitalized, no limitations on activities

Refer to [Instructions and Abbreviations] of title pages for further definition

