	To evaluate other Clinical Benefit of treatment with CX-4945 relative to the control arm	
• All-cause mortality status – the number of deaths occurred in each treatment group from Randomization (Day 1) through Day 60.• Number of respiratory failure (i.e., need for mechanical ventilation, ECMO, noninvasive ventilation, or high-flow nasal cannula oxygen delivery) occurred in each treatment group from Randomization (Day 1) through Day 45.• Number of patients hospitalized in each treatment arm from Randomization (Day 1) to Day 45• Number of days to normalization of oxygen saturation level measured by pulse oximeter at Randomization (Day 1), Day 4, Day 8, Day 11, Day 14, Day 28 and Day 45 and categorized as <96% versus ≥96%. Proportion of patients with disease progression or improvement in health status occurring from Randomization (Day 1) to Day 28. Disease progression is defined as change in patient health status assessment from item 7 to items 1- 6 and health improvement -as change from item 7 to item 8, evaluated by the ordinal NIAID 8-Point Clinical Progression Outcomes scale collected at every visit from Day 1 through Day 45. 
The 8-category ordinal scale of patient health status ranges from:
 
1. Death;2. Hospitalized, on invasive mechanical ventilation or extracorporeal membrane oxygenation (ECMO);

		
3. Hospitalized, on non-invasive ventilation or high flow oxygen devices;4. Hospitalized, requiring supplemental oxygen;5. Hospitalized, not requiring supplemental oxygen - requiring ongoing medical care (COVID-19 related or otherwise);6. Hospitalized, not requiring supplemental oxygen - no longer requires ongoing medical care;7. Not hospitalized, limitation on activities and/or requiring home oxygen;8. Not hospitalized, no limitations on activities. 
• Changes in EQ-D5-5L (used as an indicator of symptom improvement) from randomization (Day 1) to Day 8, Day 14 and Day 28.
	To evaluate changes in inflammatory markers	
• Changes in plasma IL-6 level from randomization (Day 1) to Day 4, 8, 11, and 14.• Changes in CRP, LDH, CPK, ferritin, D-dimer from randomization (Day 1) to Day 4, 8, 11, and 14.

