1.2. SCHEMA

1.3. SCHEDULE OF ACTIVITIES (SOA)

Table 1: Schedule of Activities

Procedure/Assessments	Screening Visit	Treatment Phase					Follow-Up ^[14]				
		Day	SV	Day 1 (Baseline)	Day 4	Day 8	Day 11	Day 14 (EOT)	Day 28	Day 45	Day 60
Window Period	D-7 to Day -1			within 7 days after SV	±1 day	±1 day	±1 day	±1 day	±3 days	±3 days	±3 days
Informed Consent [1]		X									
Eligibility Evaluation [2]		X									
Patient Demographics		X									
Medical History [3]		X									
Physical Examination		X	X[4]		X[4]		X[4]	X[4]	X[4]	X[4]	
Vital Signs [5]		X	X	X	X	X	X	X	X	X	
Assessment of COVID-19-related Symptoms [6]	X	Assessed Daily from Day 1-Day 14					X	X			
EQ-D5-5L			X		X		X	X			
Clinical Status - Ordinal 8-point Scale Assessment	X	X	X	X	X	X	X	X	X	X	
Pulse Oxygen Saturation (SpO2)	X	X	X	X	X	X	X	X	X	X	
ECG	X						X				
Laboratory Tests:											
Hematology [7]	X	X	X	X	X	X	X	X	X	X	
Blood Chemistry [8]	X	X	X	X	X	X	X	X	X	X	
Coagulation [9]	X	X	X	X	X	X	X	X	X	X	
Serum/Urine Pregnancy Test [10]	X						X				
Urinalysis [11]	X	X	X	X	X	X	X	X	X	X	
IL-6 levels			X	X	X	X	X				
Nasopharyngeal Swab Sample Collection [12]	X	X		X		X	X				
Randomization [13]		X									

IP Administration (Arm A only)		Arm A: CX-4945 1000 mg BID (Day 1-Day14)									
SOC/Supportive care (Arm A and Arm B)	X (as needed)										
Mortality Status		X	X	X	X	X	X	X	X	X	
Concomitant Medications	X	X	X	X	X	X	X	X	X		
Adverse Events		X	X	X	X	X	X	X	X	X	

- [1] Informed consent must be obtained prior to patient participation in any protocol-related activities that are not part of routine care.
- [2] Initial evaluation of patient eligibility will be performed by Investigator.
- [3] Medical history and current therapies (medications and non-medications).
- [4] Symptom-directed physical examination
- [5] Vital signs will include blood pressure, heart rate, respiration rate, and temperature.
- [6] Common COVID-19-Related Symptoms (see Appendix 3) should be assessed by patients daily from Day 1 through Day 14/EOT and at Day 28 and Day 45 Follow-up visits..
- [7] Hematology: Hemoglobin, Hematocrit (HCT), Red Blood Cells (RBC), White Blood Cells (WBC) with total and differential count, Absolute Neutrophil Count (ANC) and platelets.
- [8] Blood Chemistry:
 - Hepatic function indicators: total bilirubin, alkaline phosphatase (ALP), aspartate aminotransferase (AST), alanine aminotransferase (ALT), total protein, albumin, lactate dehydrogenase (LDH)

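### The ITT Death row of SAP table 14.2.4.1 uses only the NIAID scale, collected to Day 45, so it leaves Days 46–60 of the protocol's Day 60 mortality endpoint uncovered (minor)

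*SAP*

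**What the plan says.** **Protocol.** The synopsis defines the mortality endpoint as "the number of deaths occurred in each treatment group from Randomization (Day 1) through Day 60", and Section 3 repeats it. Section 9.7.1.1 makes ITT the primary population for secondary efficacy endpoints. The hospitalization endpoint in the synopsis is "Number of patients hospitalized in each treatment arm from Randomization (Day 1) to Day 45", and the synopsis sets the same Day 45 limit for respiratory failure. The 8-point scale is "collected at every visit from Day 1 through Day 45".

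Deaths also have their own data source. The Schedule of Activities has a separate row, "Mortality Status", and Section 8.2.1.2 has the investigator follow AEs, SAEs and mortality status at Days 28, 45 and 60.

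**SAP.** Table 14.2.4.1 (ITT and PP) opens with a combined row, "Subjects with any below [Event#:Subj", above three event rows:

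- "Death (NIAID item 1"
- "Respiratory Failure (NIAID item 2~3 or from AE"
- "Hospitalized (NIAID item 2~6"

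The by-visit block below them stops at Visit 8 (Day 45). SAP Section 1 says that the methods follow the protocol apart from the exceptions and clarifications it then describes. None of these shortens the mortality window.

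**The concern.** The Death row is the natural place for a reader to look for the ITT mortality result, but its only named source stops being collected about two weeks before the endpoint closes. A death after Visit 8 would be absent from that row and, unless it was counted there as another event, from the combined row.

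Mortality status is followed to Day 60 for exactly this purpose, yet no table in the SAP text available uses it. Nothing suggests that the shorter window was intended, so it looks like an oversight. The practical risk is an efficacy table and a safety table that disagree on the number of deaths in the same patients. With about 10 patients per arm, one patient is 1/10, or 10 percentage points.

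The three rows also differ in source. Respiratory Failure adds adverse events to the scale, whereas Hospitalized does not. Whether that matters depends on what a scale score describes, which the documents do not say.

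**Working it through.** The plan gives no figure to reproduce here. The check compares sources and windows, then counts days.

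**1. Source and window of each event row**

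| Row in 14.2.4.1 | Source named in the SAP | Last day of the source | Protocol endpoint ends |
|---|---|---|---|
| Death | scale item 1 | Day 45 (scale) | Day 60 |
| Respiratory Failure | scale items 2–3, or AE | Day 45 (scale); final visit (AE) | Day 45 (synopsis) |
| Hospitalized | scale items 2–6 | Day 45 (scale) | Day 45 |

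The Day 45 limit for the scale rests on the synopsis and Section 3. The by-visit list of the SAP table agrees with them. The visit marks in the Schedule of Activities are not legible enough in the available text to be relied on. AE reporting runs to the end of the final study visit (Protocol 8.3.4).

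**2. Days of the mortality window not covered**

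Uncovered days = 60 − day of Visit 8. The SAP visit table allows Visit 8 on Day 45 ± 3.

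- Visit 8 on Day 42: 60 − 42 = 18 days; 18/60 = 30%
- Visit 8 on Day 45: 60 − 45 = 15 days; 15/60 = 25%
- Visit 8 on Day 48: 60 − 48 = 12 days; 12/60 = 20%

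These are shares of calendar time. The documents give no late death rate, so no share of deaths follows.

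**3. Who could be missing from the safety table as well**

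Table 14.3.1.1 has Grade 5 and fatal SAE rows by arm. The SAP's Safety population is everyone given at least one dose of CX-4945 plus everyone randomized to standard of care. ITT minus Safety is therefore Arm A patients who were randomized but never dosed. A death is absent from both 14.2.4.1 and 14.3.1.1 only if the patient was in that group and died after Visit 8.

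**4. Hospitalized row, only if a score means status on the visit day**

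Nominal scale visits after baseline are Days 4, 8, 11, 14, 28 and 45. The open days between successive visits from Day 1 are:

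- 4 − 1 − 1 = 2
- 8 − 4 − 1 = 3
- 11 − 8 − 1 = 2
- 14 − 11 − 1 = 2
- 28 − 14 − 1 = 13
- 45 − 28 − 1 = 16

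As an assumed example, take a stay covering 5 days, s to s + 4:

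- Starts on Days 2–14: 0 of 13 avoid every nominal visit. This holds on nominal days only. With Visit 3 on Day 3 and Visit 4 on Day 9, both allowed, a stay on Days 4–8 touches no visit.
- Starts on Days 15–45: s = 15–23 (9 starts) and s = 29–40 (12 starts) avoid every nominal visit, so 9 + 12 = 21 of 31.

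With the visit windows, the Day 14–28 gap runs from 9 to 17 open days and the Day 28–45 gap from 10 to 22. If the score instead records the worst status since the last visit, no stay is missed.

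**The case against.** **Deaths to Day 60 are already reported.** AE and SAE reporting runs to the final visit. Table 14.3.1.1 shows fatal events by arm, and 14.3.1.7 repeats SAEs by criterion. A reader might infer from the Death row that the SAP loses late deaths altogether. The documents do not support that: the gap is in one row of the efficacy output. Even an undosed Arm A patient who died late should appear among the non-completers in ITT table 14.1.2, whose list of reasons is open-ended, and in the patient listings. This stands, and it is why the point is minor. It does not give the protocol endpoint a named ITT summary.

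**The row states no cut-off day.** The visit list ending at Visit 8 governs the by-visit block, not the event rows above it. This is correct, but it does not rescue the row: the only source named for Death is a scale that the protocol collects no later than Day 45.

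**The SAP text is incomplete.** Some pages and the section 16 instructions are not available. The statement that no table uses mortality status is therefore limited to the text at hand.

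**The Hospitalized row may be sound.** The protocol names no source for that endpoint, and scale items that mean hospitalized are a reasonable choice. A reader might infer from the missing AE source that admissions will be undercounted. That is not established, because it depends on the unstated recall period. Unscheduled visits, or an end-of-treatment visit held early, could also catch a stay. Any admission that meets the SAE definition appears in 14.3.1.1 too, although that table has no Day 45 cut-off. This part stands only as a conditional point.

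**Conclusion.** The Death row is wrong as written for the endpoint the protocol defines. It leaves 15 of 60 nominal days uncovered (12 to 18 with the Visit 8 window), and the SAP does not declare this as a departure from the protocol. A reader might take the 25% as a share of deaths missed, but it is calendar time only; in about 20 outpatients the number of late deaths may well be zero.

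Severity is minor, because the safety tables carry the same deaths for nearly the same patients. What remains is a possible disagreement between tables and the lack of an ITT summary of deaths to Day 60. Confidence is high for the Death row. It rests on the scale being collected no later than Day 45, as the synopsis and Section 3 both state.

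The Hospitalized point is secondary. It holds only if the score is visit-day status, and then mainly after Day 14.

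**What to change.** In SAP table 14.2.4.1:

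1. **Death.** Define it as Mortality Status or a fatal SAE from Day 1 through Day 60.
2. **Windows.** Footnote the window of each event row (Death to Day 60; Respiratory Failure and Hospitalized to Day 45), and state that the combined row mixes these windows.
3. **Hospitalized (secondary).** Add adverse events as a second source, as the Respiratory Failure row does. Count any SAE that meets the hospitalization criterion, using the criteria as recorded, before the rule in 14.3.1.7–14.3.1.8 that counts a fatal or life-threatening admission under the graver category only. The hospitalization must fall on or before Day 45. Date it by admission if that date is recorded, otherwise by SAE onset as a stated proxy. The proxy is imperfect: an event that starts on Day 44 with admission on Day 47 would count. With this source added, the row no longer depends on the recall period of the score.

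The cost is a few lines of SAP wording, some programming, and reconciliation of SAE dates with scale scores. Mortality status and SAEs are already followed to Day 60, so no new data and no protocol amendment are needed.
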